13.2.2 Planned recruitment rate

We estimate that for 3 healthcare providers to take 12 oxygen saturation measurements will take up to one day. The expert will be taking oxygen saturation readings in parallel. Therefore, allowing for healthcare provider availability and patient turn-over on the inpatient wards, we anticipate recruitment to take a maximum of 3 weeks.

13.3 Statistical analysis plan

13.3.1 Primary outcome analysis

We will calculate the proportion of readings that meet the target product profile requirement of 95% stable readings within 60 seconds. Differences in the proportion of successful readings will be compared between the expert and healthcare providers, between different age groups of children, and between the UK, Bangladesh and Malawi. This will be done using χ^2 tests. All descriptive analyses will be done using Stata 14.

13.3.2 Secondary outcome analysis

We will describe the time to stable reading, looking at the median time and inter-quartile range. We will compare these descriptive statistics between patient age groups, expert and healthcare provider participants, and with measurements from Malawi and Bangladesh. We will look for statistical differences between these sub-groups using t-tests. Descriptive analysis of the observational data on usability, including correct positioning and number of re-positions of the probe, will be conducted. Qualitative questionnaire data will be analysed using an inductive thematic approach.

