The secondary objective is to provide further description of the 'usability' of the redesigned oximeter and probe in children aged 0-59 months by healthcare workers, to assess how well children tolerate the probe, and the difference in time to a stable oximetry reading for expert users and healthcare workers in different settings, or for different ages of children.

Type of study: Mixed methods observational usability testing

Study design and methods: This observational usability testing involves three types of data collection from three sites in the UK, Malawi and Bangladesh. This protocol relates specifically to the UK testing at Great Ormond Street Hospital.

Expert usability testing: the probe and oximeter will be used by an expert on 204 stable children (i.e. not physiologically unstable or admitted to a high-dependency or intensive care unit) of different ages and with varying illness states. Children will be purposefully recruited from inpatient wards to meet age criteria by a clinical researcher. Following consent, an oxygen saturation measurement will be done by the expert user. An independent observer will note the condition of the child, along with other key demographic, performance and clinical features and the time to successful measurement of oxygen saturation.

Healthcare provider usability testing: the probe and oximeter will be used by healthcare providers on healthy or mild systemically ill patients (i.e. with a normal oxygen saturation, i.e. >94%). Children will be purposefully recruited from inpatient wards to meet age requirements by a clinical researcher and pre-screened for their oxygen saturation. 17 healthcare workers will be assessed for their performance with the prototype probe. Each HCW will undertake an oxygen saturation measurement on 12 children (maximum 204 children at Great Ormond Street Hospital). An independent observer will note the condition of the child, along with other key demographic, performance and clinical features and time to successful measurement of oxygen saturation.

Usability Questionnaire: HCW will be asked to complete a usability questionnaire to collect quantitative and qualitative feedback about the oximeter and probe usability. The questionnaire will be completed following the usability testing by all the healthcare providers.

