Study duration per participant:	Healthcare providers are the main study participants and will be involved in the study between 1 and 4 hours, with each healthcare provider taking 12 oxygen saturation measurements.
	Children will be involved in the study intermittently for up to 80 minutes. Children will be assessed for recruitment and consented prior to each measurement.
Estimated total study duration:	4 weeks
Planned study sites:	Great Ormond Street Hospital [single-site]
Total number of participants planned:	17 healthcare providers, and up to 408 children aged 0-59 months
Main inclusion/exclusion criteria:	The study will be conducted in the inpatient wards of Great Ormond Street Hospital, with recruited healthcare providers and children aged 0-59 months. Inclusion: 
- Children aged 0-59 months in an inpatient ward at Great Ormond Street Hospital- Healthcare provider working on an inpatient ward at Great Ormond Street Hospital Exclusions: 
- Children aged >59 months- Children in critical condition- Guardians lacking capacity to give informed consent for their child- Guardians unable to speak English
Statistical methodology and analysis:	We will calculate the proportion of readings that meet the target product profile requirement of 95% stable readings within 60 seconds. We will describe the time to stable reading, looking at the median time and inter-quartile range. We will compare these descriptive statistics between patient age groups, expert and healthcare provider participants, and with measurements from sites in Malawi and Bangladesh. We will describe differences between these sub-groups using t-tests. Qualitative questionnaire data will be analysed using an inductive thematic approach.

3 Introduction

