Healthcare provider usability testing: the probe and oximeter will be assessed on healthy or mild systemically ill patients (with a normal oxygen saturation, i.e. >94%). Children will be purposefully recruited from inpatient wards at GOSH to meet age requirements by a clinical researcher, who will pre-test children to ensure that their oxygen saturation is above 94% at the point of recruitment. Healthcare providers will be purposefully recruited in each site to have a range of pulse oximeter

experiences and qualifications. Healthcare providers and attending guardians will be given study information and asked for informed consent.

Following consent, the healthcare provider will take an oxygen saturation measurement. An independent observer will note the condition of the child, along with other key demographic, performance and clinical features, and time to successful measurement.

The end point for a successful reading is defined as the time from when the probe is placed on the child to when the reading is stable (one full screen of a stable pulse waveform); the user says 'STOP' at this point. The time for the successful reading, and the total time taken to obtain a reading including the number of attempts to obtain the reading will be recorded.

Usability Questionnaire: A usability questionnaire, which will provide a subjective rating of a product's usability, will be used to gather quantitative and qualitative measures of the new probes usability from the healthcare providers. The questionnaire will be conducted following the usability testing.

6 Selection of Subjects

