13.2 Sample size and recruitment

13.2.1 Sample size calculation

To calculate 95% of measurements being stable within 60 seconds (as per the target product profile) with 2.5% precision and 95% confidence intervals requires 292 measurements. This is calculated using the standard formula to calculate a sample size for estimating a proportion:

$$n \geq (Z^2 \times p(1-p))/e^2$$

(Z = confidence interval; p = expected true proportion; e = desired precision, half the desired CI width)

$$n \geq (0.95^2 \times 0.95(1-0.95))/0.025^2$$

$$n \geq 292$$

The FDA HF/UE guidance and IEC 62366 state that at least 15 participants should be included from each identified user group interacting with the device. We intend to include 17 trained healthcare workers from a high-income setting, and 17 from each of two low-income settings where there is a high burden of disease in children, and where the Lifebox pulse oximeter is supplied. Each end-user will take 12 measurements (3 from each of four different age-group stratifications of children). This gives a total of 204 measurements from each user-type in each setting. In addition to our pooled primary analysis, this will give us enough power to conduct pooled stratified analyses by site and age group.

The primary outcome will be a pooled analysis from all the participating sites, stratified by expert user and healthcare provider. Studying this number of healthcare workers will give the study sufficient power to undertake sub-group analysis by site and by age of the children assessed.

A summary of the stratified analyses is presented in the table below:

Primary Analysis	GOSH	Malawi	Bangladesh	Total (2 sites)	Total (3 sites)
Healthcare providers	204	204	204	408	612
Expert users	204	204	204	408	612
All measures	408	408	408	816	1,224
Sub-Analysis					
Neonates (HCW + expert)	102	102	102	204	306
Infants (HCW + expert)	102	102	102	204	306
Toddler (HCW + expert)	102	102	102	204	306

1. For an online calculator:

<http://epitools.ausvet.com.au/content.php?page=1Proportion&Proportion=0.95&Conf=0.95&Precision=0.025&Population>

Child (HCW + expert)	102	102	102	204	306
----------------------	-----	-----	-----	-----	-----

*shaded cell indicates sufficient power

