13.3.3 Sensitivity and other planned analyses

We will collect limited data on the number of children in whom we were unable to take measurements, recording their age and clinical condition to compare with those who we were able to take a measurement. We will compare the age distribution between the two groups, to give an indicator of age-bias in successful measurements.

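### Time to stable reading is compared by t-tests over four age groups and three sites with no overall test, and the site and user-type comparisons ignore that each user gives many readings

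*Combined protocol and SAP*

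**What the plan says.** Section 13.3.2 describes time to stable reading by median and inter-quartile range, compares it by age group, by expert or healthcare provider, and with Malawi and Bangladesh, and then states: "We will look for statistical differences between these sub-groups using t-tests". The statistical paragraph of the section 2 summary is softer: "We will describe differences between these sub-groups using t-tests". Neither place names an overall test, the pairs to be compared, a significance level or a multiplicity rule.

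The readings are grouped by user. Section 13.2.1 has 17 healthcare workers at each of three sites and says: "Each end-user will take 12 measurements (3 from each of four different age-group stratifications of children". On the expert side, the summary says for Great Ormond Street Hospital (GOSH) that "the probe and oximeter will be used by an expert on 204 stable children", and section 13.2.2 says "The expert will be taking oxygen saturation readings in parallel". Section 13.3 does not mention repeated readings by the same user.

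Section 5 records time over repeated attempts: "the total time taken to obtain a reading including the number of attempts to obtain the reading will be recorded". For children never measured, section 13.3.3 says "We will collect limited data on the number of children in whom we were unable to take measurements" and compares ages, but gives no rule for the time analysis.

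**The concern.** A t-test compares two groups, but age has four and site has three. Without an overall test, the analyst must choose pairs, and each extra pair adds a chance of a false difference. Readings by the same person also tend to be alike. A t-test that treats 204 readings from 17 workers as 204 independent results gives too small a standard error wherever users differ between the groups compared.

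Whether time differs by user, setting and age is part of the secondary objective in section 4 and appears in two secondary outcomes in section 13.1.2. Section 13.2.1 also claims enough power for analyses by site and age, so the results are meant to be interpreted. A reported site or user-type difference could reflect a few individuals.

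**Working it through.** **The plan's own figure.** Section 13.2.1 gives 292 readings. With Z = 1.96, p = 0.95 and e = 0.025, n = 1.96² × 0.95 × 0.05 / 0.025² = 291.96, rounded up to 292. (The printed substitution puts 0.95 in place of Z, which would give 68.6.) This is the precision of one proportion from independent readings. The plan gives no calculation for the t-tests.

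**Inputs from section 13.2.1.** 17 workers × 12 readings = 204 per site, and 612 over three sites. Experts also give 204 per site, 612 in all. Each worker measures 3 children in each of four age groups, so workers supply 17 × 3 = 51 of the 102 readings per age group per site and experts supply the other 51.

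**Assumed, because the documents do not say.** Two-sided 5% level; no true difference; user ICC of 0.05 or 0.10 on log time. For simulation, times are log-normal with median 20 s and log-SD ln(60/20)/1.645 = 0.668, which puts 95% of readings within 60 s.

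**1. Number of tests, independent readings.** Age has 6 pairs and site has 3. If tests were independent, the chance of any false difference would be 1 − 0.95⁶ = 26.5% for age and 1 − 0.95³ = 14.3% for site. Pairs share groups, which lowers this. Simulation gives:

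| Comparison | Any false difference |
|---|---|
| Age, six pairs | 20% |
| Site, three pairs | 12% |
| UK v each other site | 9% |
| UK v both others combined | 5% |

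**2. Clustering, site comparisons on healthcare-worker readings.** Design effect = 1 + (12 − 1) × ICC, which is 1.55 at ICC 0.05 and 2.10 at 0.10. The 204 readings per site are then worth 204/1.55 = 132 or 204/2.10 = 97. For a single contrast the true error is about 2 × [1 − Φ(1.96/√1.55)] = 11.5%, or 17.6% with 2.10. Simulation on the seconds scale gives:

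| Test | ICC 0.05 | ICC 0.10 |
|---|---|---|
| Any of three site pairs | 23% | 33% |
| UK v both combined | 10% | 15% |
| Overall Kruskal-Wallis on single readings | 14% | 24% |
| Overall F-test on worker means (17 v 17 v 17; normal data) | 5.2% | 4.9% |

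An overall test alone therefore does not repair the site comparison. It must also allow for the user.

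**3. Clustering, expert v healthcare worker.** With k experts in total, the variance of the difference relative to what the t-test assumes is (1 − ICC) + ICC × 306 × (1/51 + 1/k) = (1 − ICC) + ICC × (6 + 306/k).
- One expert per site (k = 3): 0.95 + 0.05 × 108 = 6.35, and 0.90 + 0.10 × 108 = 11.70. The error 2 × [1 − Φ(1.96/√ratio)] is 44% / 57%. Simulation in seconds gives 41% / 55%.
- Four experts per site (k = 12): 0.95 + 0.05 × 31.5 = 2.525, and 0.90 + 0.10 × 31.5 = 4.05. The formula gives 22% / 33%, and simulation 18% / 30%.

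**4. Clustering, age.** Each worker contributes equally to every age group, so the worker effect cancels in the difference. A single age-pair t-test on healthcare-worker readings has a simulated error of 5.0% / 4.2%. The excess for age comes only from the number of pairs.

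**The case against.** The strongest reply is that this is a secondary outcome, that the summary speaks only of describing differences, and that the plan never says it will test every pair. Comparing with Malawi and Bangladesh can be read as UK against the rest, and that single contrast has a 5% error if readings are independent. The ICC is assumed throughout. The number of experts is unclear: the summary and section 13.2.2 use the singular, while section 4 and others speak of expert users.

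Much of this stands, and it limits the size of the problem. It does not remove it. Section 13.3.2 looks for statistical differences, and a t-test is inferential whatever verb introduces it. With clustering, even the single UK contrast runs at 10% / 15%. With four experts per site the user-type test still runs well above 5%.

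A reader might also infer that repeated readings per worker inflate the age comparisons. The design in section 13.2.1 rules that out for the worker effect, since every worker covers all four age groups. Nor do the documents show that t-tests must give way to rank tests: the errors shown come from multiplicity and clustering, not from skewed times.

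A reader might further infer that unmeasured children bias the time comparison in favour of the worse group. That needs extra assumptions about who fails. Section 13.3.1 also plans a test of success ("Differences in the proportion of successful readings will be compared between the expert and healthcare providers"), which would largely show a failure gap if failed attempts count as non-success.

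**Conclusion.** The point holds as two separate errors in a secondary analysis. Multiplicity affects age and site: about 20% and 12% if all pairs are tested, less otherwise. Clustering affects site and user type: about 23% / 33% for any site pair, and from 18% / 30% (four experts per site) to 41% / 55% (one per site) for expert v healthcare worker.

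These rates rest on a 5% level and an ICC of 0.05 / 0.10. One expert per site is how the text reads for GOSH and is assumed for the other two sites, so the upper figures should not be quoted without that condition. The primary proportion is unaffected and no decision rule depends on these comparisons. The change is worth making because it is cheap, but the study does not depend on it.

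**What to change.** Replace the t-tests in section 13.3.2 and the summary with one overall test per factor that allows for the user, before any pairwise contrast. Two workable forms are:
- a mixed model on log time with a random effect for user and terms for age group, site and user type;
- for site alone, an overall test on each healthcare worker's mean (17 v 17 v 17). This is the form for which the error of about 5% was checked; the mixed model was not simulated.

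Keep the planned age analysis that combines healthcare-worker and expert readings. State how many experts there are per site and record which expert took each reading. If there is one or only a few per site, report the expert v healthcare-worker difference as an estimate without a significance claim, since the person cannot be separated from the expertise. State that times are among successful readings, and show the failure proportion by group beside them.

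The cost is SAP wording and a user identifier on each reading; section 11.1 already assigns one to healthcare providers. The downside is wider intervals and lower power for site comparisons, in line with the 132 or 97 effective readings per site shown above.

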13.3.3 Sensitivity and other planned analyses

We will collect limited data on the number of children in whom we were unable to take measurements, recording their age and clinical condition to compare with those who we were able to take a measurement. We will compare the age distribution between the two groups, to give an indicator of age-bias in successful measurements.

13.4 Name of Committees involved in trial

There will be structured oversight and reporting of the project. A Project Management Group (PMG), chaired by the CI will be overseeing the study. This committee will also serve the function of the Data Monitoring Committee, with expertise in observational studies and statistics.

We have set up a project advisory group composed of international experts in pulse oximetry who have given input into the design and monitoring of the project and will be invited to provide feedback on the redesigned oximeter probe. They will be given regular updates on the progress of the study, and will act as an independent advisory committee.

We have also involved the GOSH Patient and Public Involvement and Engagement (PPI/E) Team, for input into the study documents, and will feedback results from the study.

14 Direct Access to Source Data/Documents

The investigators will permit study-related monitoring, audits, REC review, and regulatory inspection, providing direct access to study documents. Study participants will be informed of this during the informed consent discussion.

15 Ethics and regulatory requirements

The sponsor will ensure that the study protocol, patient information sheet and consent form have been approved by the MHRA, HRA and research ethics committee, prior to any patient recruitment. The protocol and all agreed substantial protocol amendments, will be documented and submitted for ethical and regulatory approval prior to implementation. Within 90 days after the end of the study, the CI will ensure that the REC and MHRA are notified that the study has finished. If the study is terminated prematurely, those reports will be made within 15 days after the end of the study. The CI will supply the Sponsor with a summary report of the study, which will then be submitted to the MHRA and REC within 1 year after the end of the trial.

16 Monitoring

The sponsor will determine the appropriate level and nature of monitoring required for the trial. Risk will be assessed on an ongoing basis and adjustments made accordingly. The degree of monitoring will be proportionate to the risks associated with the trial. A trial specific oversight and monitoring plan will be established for studies. The trial will be monitored in accordance with the agreed plan.

17 Finance

The study is funded by the Bill and Melinda Gates Foundation [grant code: OPP1133291]. The CI and all co-investigators declare no competing financial interests.

